5. INCLUSION/ EXCLUSION CRITERIA

- A. Adult (18 years or older) patients being treated with Mohs micrographic surgery will be included in this study.
- B. Surgical procedure must include one of the following:
 - a. Any defect being healed by granulation
 - i. Including periocular defects²²
 - ii. Including defects with fenestrated cartilage^{20,21}
 - iii. Including skin graft donor sites left to heal by granulation
- C. Patients must not

- a. be pregnant or breastfeeding
 - i. urine qualitative pregnancy test will be obtained in-office, prior to surgery, from women of childbearing potential
 - ii. pregnancy test not required on post-menopausal women or women with history of tubal ligation, ablative uterine procedure or salpingo/oophorectomy
- b. Have a known allergic reaction or sensitivity to TXA
- c. Have an international normalized ratio (INR) out of therapeutic range if on warfarin; all patients on warfarin will be tested within one week of surgery
 - i. INR level will be obtained within 1 week prior to time of intervention
 - ii. therapeutic range INR 2.0-3.0
 - iii. if high-risk prosthetic heart valve, therapeutic range INR 2.5 – 3.5

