- IX. Post-operative bleeding complications will be determined using the following data points (see Appendix II):
 - a. Did patient call with concern for post-operative bleeding on the same day of surgery, or post-operative day 0 (POD0)? YES/NO
 - b. Did patient call with concern for post-operative bleeding on POD1? YES/NO
 - c. Did patient call with concern for post-operative bleeding on POD2? YES/NO
 - d. Did patient return to clinic within post-operative days 0-2 for evaluation of post-operative bleeding complication? YES/ NO
 - e. Did patient receive postoperative intervention of any kind for hemorrhagic complication? YES/NO
 - f. Type of intervention performed for bleeding complication.
 - g. Perceived side-effects, if any, by patient due to study intervention.
- X. Study patients will be called 3 days after their surgical procedure to be asked the above data points in case a patient received outside care that was not disclosed to office or research staff.
- XI. Patients' medical charts will be reviewed for and patients will also be asked to divulge the following medical history for demographic and sub analysis purposes (see AppendixIII):
 - a. Age, sex, race
 - b. Medical history including hypertension, coronary vascular disease, liver disease, renal disease
 - c. Medications including anti-platelet agents and anti-coagulants

B. Study duration and number of study visits required of research participants.

- I. Duration sufficient to enroll 124 patients (62 per treatment arm). No additional patient visits will be required beyond the visit normally required for their procedure and/or suture removal.
- II. The initial visit for this study will take place after already scheduled Mohs micrographic surgery which will take no longer than one additional hour during the surgical visit.

- III. Participation includes a total of three days, specifically postoperative days 0-2.
- IV.
- C. Blinding, including justification for blinding or not blinding the trial, if applicable.
 - I. Double-blinded trial in which patients and surgeons will be masked to which treatment arm participants are assigned
- D. Justification of why participants will not receive routine care or will have current therapy stopped.
 - I. Care will be identical in both arms except for addition of topical application of TXA vs normal saline soaked gauze to wound bed at completion of MMS.
- E. Justification for inclusion of a placebo or non-treatment group.

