6. DRUGS/ SUBSTANCES/ DEVICES

- A. Active intervention group: application of TXA soaked gauze on open wound defect, held in place by standard postoperative pressure bandage
- B. Control group: Identically placed sterile normal saline soaked gauze, held in place by standard postoperative pressure bandage

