7. STUDY STATISTICS

- A. Primary outcome variable.
 - I. Determination of effects of topical TXA on postoperative hemorrhagic complications and need for additional visits for care related to bleeding complications within the first 2 days following Mohs surgery with a wound allowed to heal by granulation
- B. Secondary outcome variables.
 - I. Determination of possible adverse effects, if any, that are different between the intervention and control arms.
- C. Statistical plan including sample size justification and interim data analysis
 - I. The statistical analysis will be performed by the University of Missouri biostatistics group. The sample size was calculated using a power analysis with the alpha set to 0.05 and the power set to 80%. Dichotomous variables were assessed with an anticipated change of bleeding of 10% in the intervention group and 30% in the control group based on prior clinical experience. No interim data analysis is planned.
 - II. Data will be analyzed on an intention to treat basis.
- D. Early stopping rules.
 - I. Study will end early if severe or high rate of adverse events occur.

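### The bleeding items name no wound, so the body text lets bleeding from a wound that received no study solution count toward the primary outcome

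*Combined protocol and SAP*

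**What the plan says.** **Who can enter.** Section 5.B sets the surgical condition as "Surgical procedure must include one of the following", followed by any granulating defect. The sub-list adds "Including skin graft donor sites left to heal by granulation". Nothing limits a patient to one wound or excludes a patient who also has a grafted or sutured wound. Section 4.B.I says "No additional patient visits will be required beyond the visit normally required for their procedure and/or suture removal", which fits with some participants having sutured wounds.

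**What is treated.** Section 6.A describes the active intervention as "application of TXA soaked gauze on open wound defect, held in place by standard postoperative pressure bandage". Section 4.A likewise puts the pad on the wound bed. No solution is assigned to a grafted or sutured site.

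**What is counted.** Section 4.A.IX lists the items that determine a bleeding complication. Items a to c ask about calls by day, for example "Did patient call with concern for post-operative bleeding on POD1? YES/NO". Item d asks "Did patient return to clinic within post-operative days 0-2 for evaluation of post-operative bleeding complication? YES/ NO". Item e asks "Did patient receive postoperative intervention of any kind for hemorrhagic complication? YES/NO". Under 4.A.X, the telephone call three days after surgery repeats these items. None of them names a wound or site.

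**Primary outcome.** Section 7.A covers hemorrhagic complications and extra visits for bleeding "within the first 2 days following Mohs surgery with a wound allowed to heal by granulation". That phrase describes the surgery. It does not say that only bleeding from the granulating wound counts.

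**The concern.** A graft donor site implies a graft placed somewhere else. A patient who qualifies through a granulating donor site therefore has at least two fresh wounds, and the protocol assigns solution to only one kind. A patient with one granulating defect and one sutured defect is in the same position. If such a patient calls or returns because the grafted or sutured site bleeds, the items as worded are answered yes.

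The objective in section 2 is the hemostatic effect of tranexamic acid (TXA) applied to granulating defects. Bleeding at a site without solution cannot respond to the solution. Counting it adds the same expected burden to both arms and shrinks the observed difference. It also raises the recorded rates above those of the wound type under study, and the rate of hemorrhagic complications is itself listed as an objective. If the site is not recorded when the event is reported, no analysis can recover it later.

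**Working it through.** **1. Inputs from the protocol.** 30% bleeding in control and 10% with TXA, alpha 0.05 and power 80% (section 7.C.I); 62 per arm, 124 in total (section 4.B.I). Sidedness is not stated.

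**2. Reproduce the planned size.** Two-sided test of two proportions, pooled variance under the null, no continuity correction, with mean rate 0.20:

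n = [1.960 × √(2 × 0.20 × 0.80) + 0.8416 × √(0.30 × 0.70 + 0.10 × 0.90)]² / 0.20²

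= [1.960 × 0.5657 + 0.8416 × 0.5477]² / 0.04 = 1.5697² / 0.04 = 61.6, so 62 per arm.

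This matches the protocol. Power at 62 per arm is Φ[(0.20 × √62 − 1.1087) / 0.5477] = Φ(0.851) = 80.3%.

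**3. Add bleeding from untreated wounds.** Let f be the share of patients who also have an untreated wound and q the risk that this wound bleeds in the outcome window, independent of arm and of the treated wound. The documents give neither figure, so both are assumptions. With p the treated-wound rate:

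recorded rate = p + (1 − p) × f × q

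The difference between arms becomes 0.20 × (1 − f × q).

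Example with f = 0.20 and q = 0.10, so f × q = 0.02: control 0.30 + 0.70 × 0.02 = 31.4%; TXA 0.10 + 0.90 × 0.02 = 11.8%; difference 19.6 points; ratio 0.118 / 0.314 = 0.38. Power at 62 per arm is 76.2%.

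**4. Range.** The last column is the number per arm that would restore 80% power.

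| f | q | Control | TXA | Difference (points) | Ratio | Power, 62 per arm | n per arm for 80% |
|---|---|---|---|---|---|---|---|
| 0 | – | 30.0% | 10.0% | 20.0 | 0.33 | 80.3% | 62 |
| 5% | 10% | 30.4% | 10.5% | 19.9 | 0.34 | 79.2% | 64 |
| 10% | 10% | 30.7% | 10.9% | 19.8 | 0.36 | 78.2% | 65 |
| 20% | 10% | 31.4% | 11.8% | 19.6 | 0.38 | 76.2% | 69 |
| 10% | 30% | 32.1% | 12.7% | 19.4 | 0.40 | 74.2% | 72 |
| 20% | 30% | 34.2% | 15.4% | 18.8 | 0.45 | 68.3% | 82 |

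The last row is an upper scenario: it gives the untreated wound the full bleeding rate planned for the control arm.

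**The case against.** **The text is silent, not explicit.** A reader might infer that the plan deliberately counts bleeding anywhere in the patient. No section says so. Sections 2 and 7.A both speak of granulating wounds, and a sensible investigator could take the items to mean that wound. This stands against any claim that untreated-wound bleeding will be scored. It does not remove the gap, because the items taken literally score it and no attribution rule says otherwise.

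**The form may settle it.** Section 4.A.IX refers to Appendix II, which was not available for this review. A site field there cannot be ruled out. If it exists, 4.A.IX and 7.A would still need to say which events count.

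**The planning rates may already be per patient.** Section 7.C.I gives 30% and 10% as bleeding rates from clinical experience and names no wound. If they already include bleeding at other sites, the loss of power does not follow as computed.

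**The effect may be very small.** Section 3 says bleeding complications are very low in cutaneous surgery. Its remark on grafts and flaps concerns what a hematoma can lead to, not how often one occurs. If few patients have a second wound, the loss is one or two points.

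**A per-patient count is a legitimate quantity.** Extra visits for bleeding are naturally counted per patient. It would be too strong to call such rates wrong; they answer a broader question than the one in section 2.

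**Conclusion.** The point holds as a gap in the outcome definition. The body text admits patients with an untreated second wound and does not say that only bleeding from a treated wound counts. Any such events are unrelated to arm, so in expectation they dilute the effect and favour neither arm.

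Power at 62 per arm would fall from 80.3% to between about 79% and 68% across the scenarios shown. The milder ones (79% and 78%) are at least as plausible as the upper one. The range rests on three assumptions: the share of patients with an untreated wound, that wound's bleeding risk, and 30% versus 10% being treated-wound rates.

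A reader might infer that the sample size is wrong or that the trial is biased toward one treatment. The documents support neither: 62 per arm reproduces exactly from the stated inputs, and the extra events do not depend on assignment. The change is worth making because it is cheap and because an unrecorded site cannot be reconstructed.

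**What to change.** In 4.A.IX and Appendix II:

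- Record at surgery which wound or wounds received study solution. Section 5.B sets no limit of one granulating defect, so naming a single study wound would discard genuine events in a patient with two treated defects.
- For items a to f, and in the day-3 call, ask which site each call, visit or intervention concerned.

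In 7.A, state that the primary outcome counts bleeding from any wound that received study solution. Tabulate bleeding at other sites separately by arm, so the per-patient total remains available.

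The cost is one field on the form and one question in the call script, with no added visits or patients. The small downside is that some calls will not identify the site. These need one rule, stated in advance and applied identically in both arms. For example, count them as treated-wound events and add a sensitivity analysis that excludes them. That rule lets a little of the dilution back in, which is why the sensitivity analysis is needed.

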6. DRUGS/ SUBSTANCES/ DEVICES

- A. Active intervention group: application of TXA soaked gauze on open wound defect, held in place by standard postoperative pressure bandage
- B. Control group: Identically placed sterile normal saline soaked gauze, held in place by standard postoperative pressure bandage

7. STUDY STATISTICS

- A. Primary outcome variable.
 - I. Determination of effects of topical TXA on postoperative hemorrhagic complications and need for additional visits for care related to bleeding complications within the first 2 days following Mohs surgery with a wound allowed to heal by granulation
- B. Secondary outcome variables.
 - I. Determination of possible adverse effects, if any, that are different between the intervention and control arms.
- C. Statistical plan including sample size justification and interim data analysis
 - I. The statistical analysis will be performed by the University of Missouri biostatistics group. The sample size was calculated using a power analysis with the alpha set to 0.05 and the power set to 80%. Dichotomous variables were assessed with an anticipated change of bleeding of 10% in the intervention group and 30% in the control group based on prior clinical experience. No interim data analysis is planned.
 - II. Data will be analyzed on an intention to treat basis.
- D. Early stopping rules.
 - I. Study will end early if severe or high rate of adverse events occur.

8. RISKS

- A. Medical risks, listing all procedures, their major and minor risks and expected frequency.

- I. Topical TXA application
 - a. potential local allergic reaction
- B. Steps taken to minimize the risks.
 - I. Plan for reporting unanticipated problems or study deviations.
 - a. Will report all deviations and problems to IRB.
 - II. Legal risk such as the risks that would be associated with breach of confidentiality.
 - a. Participants will be assigned a study number, which will have no identifiable information. Key to match study number with patient will be located and protected on encryption secured software with access only available to research team. Hard copy will be located in research office in locked cabinet with key only available to research team.
- III. Financial risks to the participants.
 - a. In the case of adverse events related to study, participants may incur medical fees associated with treatment of the adverse events.

9. BENEFITS

- A. Description of the probable benefits for the participant and for society.
 - I. Patients may have reduced post-operative bleeding complications and improved overall surgical experience if in the intervention arm.
 - II. If this intervention is helpful, then the intervention may serve as an additional hemostatic wound care option in cutaneous surgery to prevent postoperative bleeding complications and the costs and angst associated with such complications

